#### Vital signs

Percentage of subjects with clinical relevant changes from baseline to 2,5 hrs post-dose in SBP and DBP defined as

- Change from pre-dose in DBP > 10 mmHg;
- Change from pre-dose in SBP > 20 mmHg;

will be summarized.

### 12-lead safety ECG

Clinical Study Code: CLI-06001AA1-02	Version No.: 1.0
EUDRACT No.: 2020-004201-31	Date: 19 October 2020

Percentage of subjects with clinical relevant changes from baseline to 2,5 hrs post-dose in HR defined as

- Change from pre-dose in HR> 20 bpm

will be summarized.

### **Laboratory data**

For quantitative laboratory parameters (chemistry, haematology and fasting glucose). Shift tables from screening with reference to normal ranges will be summarized.

All laboratory data will be listed with abnormal values flagged.

### **12.3.6 Interim analysis**

Not Applicable.

## **13. ETHICS COMMITTEE/INSTITUTIONAL REVIEW BOARD APPROVAL**

The study proposal will be submitted to the Ethics Committee in accordance with the local requirements.

The EC shall give its opinion in writing -clearly identifying the study number, study title and informed consent form approved-, before the clinical trial commences.

A copy of all communications with the EC will be provided to the Sponsor.

The Investigator should provide written reports to the EC annually or more frequently if requested on any changes significantly affecting the conduct of the trial and/or increasing risk to the subjects (according to the requirements of each country).

## **14. REGULATORY REQUIREMENTS**

The study will be notified to the Health Authorities (or authorized by) according to the local legal requirements.

Selection of the subjects will not start before the approval of the Ethics Committee has been obtained and the study notified to Health Authorities (or authorized by).

## **15. INFORMED CONSENT**

Informed consent must be written in a language understandable to the subjects. It is the responsibility of the Investigator to obtain written consent from each subject prior to any study related procedures taking place, by using the latest EC approved version of the document.

Adequate time shall be given to the subject to enquire the PI about any clarification needed and to consider his or her decision to participate to the trial.

If the subject is unable to read, the informed consent will be obtained in the presence of an impartial witness, e.g., a person independent of the study who will read the informed consent form and the written information for the subject.

Consent must be documented by the subject's dated signature. The signature confirms that the consent is based on information that has been understood. Moreover, the Investigator must sign and date the informed consent form.

Each subject's signed informed consent must be kept on file by the Investigator. One copy must be given to the subject.

## **16. SOURCE DOCUMENTS/DATA**

### **16.1 Recording of source data**

Clinical Study Code: CLI-06001AA1-02	Version No.: 1.0
EUDRACT No.: 2020-004201-31	Date: 19 October 2020

Data collection is the responsibility of the clinical trial staff at the site under the supervision of the site investigator. The investigator is responsible for ensuring the accuracy, completeness, legibility, and timeliness of the data reported. All source documents should be completed in a neat, legible manner to ensure accurate interpretation of data.

Data recorded in the eCRF derived from source documents should be consistent with the data recorded on the source documents.

## **16.2 Direct access to source document/data**

The Investigators or designated must permit trial-related monitoring, audits, Ethics Committee review or regulatory inspection, providing direct access to source data/documents.

## **17. STUDY MONITORING**

Monitoring will be performed by [REDACTED] who has been designated by Chiesi.

It is understood that the monitor(s) will contact and visit the Investigator/centre before the study, regularly throughout the study and after the study had been completed, and that they will be permitted to inspect the various study records: case reports form, Investigator study file and source data, provided that subject confidentiality is respected.

The purposes of these visits are:

- to assess the progress of the study;
- to review the compliance with the study protocol;
- to discuss any emergent problem;
- to check the eCRFs for accuracy and completeness;
- to validate the contents of the eCRFs against the source documents;
- to assess the status of drug storage, dispensing and retrieval;
- Prior to each monitoring visit, the Investigator or staff will record all data generated since the last visit on the case report forms. The Investigator and/or study staff will be expected to be available for at least a portion of the monitoring visit to answer questions and to provide any missing information;
- It is possible that the Investigator site may be audited by Sponsor personnel or regulatory national and/or international regulatory agencies during and after the study has been completed.

## **18. QUALITY ASSURANCE**

The R&D Quality Assurance Department of Chiesi may perform an audit at any time according to the Sponsor's Standard Operating Procedures, in order to verify whether the study is being conducted in agreement with Good Clinical Practices and the protocol.

## **19. INSURANCE AND INDEMNITY**

Chiesi holds and will maintain an adequate insurance policy covering damages arising out of Chiesi's sponsored clinical research studies.

Chiesi will indemnify the Investigator and hold him/her harmless for claims for damages arising out of the investigation, in excess of those covered by his/her own professional liability insurance, providing that the drug was administered under his/her or deputy's supervision and in strict accordance with accepted medical practice and with the study protocol.

The Investigator must notify Chiesi immediately upon notice of any claims or lawsuits.

Clinical Study Code: CLI-06001AA1-02	Version No.: 1.0
EUDRACT No.: 2020-004201-31	Date: 19 October 2020

## 20. CONFIDENTIALITY

All study documents are provided by the Sponsor in confidence to the Investigator and his/her appointed staff. None of this material may be disclosed to any party not directly involved in the study without written permission from Chiesi.

The Investigator must assure the subject's anonymity will be maintained. The Investigator will keep a separate list with at least the initials, the subject's study numbers, names, and addresses and telephone numbers. The Investigator will maintain this for the longest period of time allowed by his/her own institution and, in any case, until further communication from Chiesi.

## 21. PREMATURE TERMINATION OF THE STUDY

Both the Sponsor and the Investigator reserve the right to terminate the study at any time. Should this be necessary, the procedures for an early termination or temporary halt will be arranged after consultation by all involved parties.

The Sponsor should submit a written notification to the Regulatory Authority concerned and Ethics Committee providing the justification of premature ending or of the temporary halt.

## 22. CLINICAL STUDY REPORT

The clinical study report, including the statistical and clinical evaluations, shall be prepared and sent to principal Investigator for agreement and signature.

At the end of the trial a summary of the clinical study report will be provided to the Ethics Committees, to the Competent Authority of the EU Member State and to Investigator.

## 23. RECORD RETENTION

After completion of the study, all documents and data relating to the study will be kept in an orderly manner by the Investigator in a secure study file.

Regulations require that essential documents must be retained for at least two years after the final marketing approval in an ICH region or until two years have elapsed since the formal interruption of the clinical development of the product under study.

It is the responsibility of the Sponsor to inform the Investigator of when these documents can be destroyed. The Investigator must contact Chiesi before destroying any trial-related documentation. In addition, all subjects' medical records and other source documentation will be kept for the maximum time permitted by the institution.

## 24. PUBLICATION OF RESULTS

Chiesi is entitled to publish and/or present any results of this study at scientific meetings, and to submit the clinical trial data to national and international Regulatory Authorities and, if they fall under the Chiesi commitments on Clinical Trial Transparency, to make them available on [www.chiesi.com](http://www.chiesi.com) website.

Chiesi furthermore reserves the right to use such data for industrial purposes.

In the absence of a Study Steering Committee, Investigators will inform Chiesi before using the results of the study for publication or presentation, and agree to provide the Sponsor with a copy of the proposed presentation. Data from individual study sites must not be published separately.

Negative as well as positive results should be published or otherwise made publicly available according to the relevant regulatory requirements.

Clinical Study Code: CLI-06001AA1-02	Version No.: 1.0
EUDRACT No.: 2020-004201-31	Date: 19 October 2020

## APPENDIX 2 – RECOMMENDATIONS RELATED TO CONTRACEPTION AND PREGNANCY TESTING IN CLINICAL TRIALS

### Definition of women of childbearing potential and of fertile men

For the purpose of this document, a woman is considered of childbearing potential (WOCBP), i.e. fertile, following menarche and until becoming post-menopausal unless permanently sterile.

### Definition of women of non-childbearing potential

For the purpose of this document, a woman is considered of non-childbearing potential (WNOCBP), i.e. sterile, when physiologically incapable of becoming pregnant (i.e. post-menopausal or permanently sterile).

- A postmenopausal state is defined as no menses for 12 months without an alternative medical cause. A high follicle stimulating hormone (FSH) level in the postmenopausal range may be used to confirm a post-menopausal state in women not using hormonal contraception or hormonal replacement therapy. However, in the absence of 12 months of amenorrhea, a single FSH measurement is insufficient.
- Permanent sterilisation methods include hysterectomy, bilateral salpingectomy and bilateral oophorectomy.

### Definition of fertile men

For the purpose of this document, a man is considered fertile after puberty unless permanently sterile by bilateral orchidectomy.

### Birth control methods, which may be considered as highly effective

For the purpose of this guidance, methods that can achieve a failure rate of less than 1% per year when used consistently and correctly are considered as highly effective birth control methods. Such methods include:

- combined (estrogen and progestogen containing) hormonal contraception associated with inhibition of ovulation:
  - oral
  - intravaginal
  - transdermal
- progestogen-only hormonal contraception associated with inhibition of ovulation:
  - oral
  - injectable
  - implantable
- intrauterine device (IUD)
- intrauterine hormone-releasing system (IUS)
- bilateral tubal occlusion
- vasectomised partner 1
- sexual abstinence 2

 Vasectomised partner is a highly effective birth control method provided that partner is the sole sexual partner of the WOCBP trial participant and that the vasectomised partner has received medical assessment of the surgical success.

 Sexual abstinence is considered a highly effective method only if defined as refraining from heterosexual intercourse during the entire period of risk associated with the study treatments. The reliability of sexual abstinence needs to be evaluated in relation to the duration of the clinical trial and the preferred and usual lifestyle of the subject.

Clinical Trial Facilitation Group guidance: Recommendations related to contraception and pregnancy testing in clinical trials. Final version 2014-09-15

Clinical Study Code: CLI-06001AA1-02	Version No.: 1.0
EUDRACT No.: 2020-004201-31	Date: 19 October 2020

## APPENDIX 3 – BREAKDOWN OF BLOOD SAMPLES COLLECTION

### Detailed Blood Collection Volumes for PK sampling:

TOTAL VOLUME TO BE COLLECTED PER SUBJECT							
	Clinical chemistry & Fasting glucose	Hematology	Serology	Whole Blood AMS	PK	PK-AMS	Metabolite profiling
Screening	1	1	1				
Day -1							
Day 1				4	12	15	15
Day 2					1	1	1
Day 3					1	1	1
Day 4					1	1	1
Day 5					1	1	1
Day 6					1	1	1
Day 7					1	1	1
Day 8					1	1	1
Day 9					1	1	1
Day 10					1	1	1
Day 11	1	1			1	1	1
Follow up							
Total vol (mL) per sample	3.5	4	3.5	2	4	5	10
Tot vol (mL)	7	8	3.5	8	88	125	250
Total vol (mL) per subject	489.5

t _{min}	Time to reach the C _{min}
V _{dss}	Volume of distribution at steady-state
V _z	Volume of distribution during the terminal phase

WHO	World Health Organisation
WHO-DD	World Health Organisation Drug Dictionary

VERSION HISTORY

Version	Date	Change History
1.0	15March2022	First version

1 Introduction

This document presents the Statistical Analysis Plan (SAP) for Chiesi Farmaceutici S.p.A. protocol CLI-06001AA1-02: Evaluation of the absolute bioavailability and mass balance of CHF6001 following a single inhaled dose co-administered with an intravenous radiolabelled microtracer dose in healthy volunteers.

This analysis plan is based on the final protocol (version 1.0, 19 October 2020) and the final electronic case report form (eCRF) (version 2.0, 02Mar2021).

The SAP provides the description of the final analyses. In case of deviations from the SAP, explanations will be provided in the Clinical Study Report (CSR).

██████████ will perform the statistical analyses and is responsible for the production and quality control of all outputs described in this document.

2 Study Design

This is a phase I, open-label, uncontrolled, non-randomized, single dose, single centre study in 8 healthy male subjects designed to evaluate absolute bioavailability and mass balance of CHF6001 following a single inhaled dose co-administered with an intravenous radiolabelled microtracer dose.

The study consists of two periods (Screening and Treatment) and Follow-up call.

Screening:

At Screening visit (31 to 3 days before first study treatment administration), subjects will be selected to enter the study according to the eligibility criteria. Study related procedures will be performed upon obtaining a signed informed consent.

Treatment Period:

During treatment period, subjects will remain at the clinical site from Day -1 until the morning of Day 11 and will be administered a single dose of CHF6001 on Day 1. 4 inhalations of CHF6001 800 μ g/20mg NEXThaler® DPI (total dose of 3200 μ g) co-administered with an intravenous microdose (18.5 μ g and 500nCi (18.5kBq)) of [^{14}C]-labelled CHF6001 will be administered. The subjects will be discharged after the 240h post-dose assessments are completed.

Follow-up:

A follow-up phone call (or visit, if necessary) will be performed between 7 to 10 days after discharge or premature discontinuation to check and record concomitant medications and the status of any unresolved adverse events or occurrence of any new adverse events (AEs).

The end of the trial is defined at execution of the Follow-up call (or visit) of the last subject of the trial.

The study plan and scheduled tests are summarised in the following flow-chart:

Table 1: Study Plan

	Screening	Treatment Period				Follow-up
		Day -1	Day 1	Day 2-10	Day 11	
Informed consent	X					
Residential period		X	X	X		
Discharge					X	
Treatment intake						
IMP administration			X ¹			
Training						
Training with In-Check Dial	X	X	X			
Training with Placebo	X	X	X			
Subject Health Evaluation						
In/Ex Criteria	X	X				
Medical History	X					
Demographic data	X					
Height and weight	X					
Alcohol breath test	X	X				
Physical examination	X	X			X ²	
Adverse Events recording	X	X	X	X	X	X
Restrictions	X	X	X	X	X	
Concomitant Med	X	X	X	X	X	X
Safety assessment in blood						
Clinical Chemistry	X				X ²	
Serology	X					
Haematology	X				X ²	
Fasting glucose	X				X ²	
Generic assessments in urine						
Urinalysis	X					
Drug panel	X	X				
Cotinine	X	X				
Samples for PK evaluations ^a						
Blood			X	X	X	
Urine		X	X	X	X	

	Screening	Treatment Period				Follow-up
		Day -1	Day 1	Day 2-10	Day 11	
Feces		X	X	X	X	
Cardiac assessments^b						
Local ECG	X		X			
Vital Signs - Blood Pressure	X		X			
Pulmonary Assessment						
Spirometry	X					

Footnotes for Evaluation Schedule:

1. There will be 2 types of administration:
 - 4 inhalations of CHF6001 800 μ g/20mg DPI NEXThaler[®]
 - Intravenous infusion for 15min of the tracer starting 1h45min after the inhaled dose (time of the first inhalation) and ending at the expected T_{max} of 2 h for the inhaled dose
2. A full physical examination and collection of blood safety test will be performed at discharge. A follow-up visit will be done only if deemed necessary by the principal investigator.

a) Pharmacokinetic samples will be collected as:

- **Blood samples** for plasma non-radiolabeled CHF6001 to be collected at pre-dose (within 60 min from inhaled dosing) and at the following timepoints post inhaled dose: **15, 30, 60, 90 min, 2, 3.75, 5.75, 7.75, 9.75, 11.75, 13.75, 25.75, 49.75, 73.75, 97.75, 121.75, 145.75, 169.75, 193.75, 217.75 and 241.75 hours.**
- **Blood samples** for plasma [¹⁴C]-total, [¹⁴C]-CHF6001, [¹⁴C] of the relevant metabolites to be collected at pre-dose (within 60 min from inhaled dosing) and at the following timepoints relative to the start of the IV infusion: **5, 10, 15 [end of infusion], 20, 25, 30, 45, 60 min, 2, 4, 6, 8, 10, 12, 24, 48, 72, 96, 120, 144, 168, 192, 216 and 240 hours.**
- **Blood samples** for whole blood [¹⁴C]-total and [¹⁴C]-CHF6001 at pre-dose (within 60 min from inhaled dosing) and **20 min after start of infusion**
- **Urine samples** for assessments of [¹⁴C]-total, [¹⁴C]-CHF6001 and [¹⁴C] of the relevant metabolites to be collected at pre-dose from -12 hours to immediately before study drug inhaled administration (-12-0h) and at the following time frames relative to the start of the IV infusion: **0-4h, 4-8h, 8-12h, 12-24h, 24-48h, 48-72h, 72-96h, 96-120h, 120-144h, 144-168h, 168-192h, 192-216h and 216-240h.**
- **Fecal samples** for assessments of [¹⁴C]-total, [¹⁴C]-CHF6001 and [¹⁴C] of the relevant metabolites to be collected at pre-dose from check-in (Day -1) to immediately before study drug inhaled administration (check-in -0h) and at the following time frames relative to the start of the IV infusion: **0-24h, 24-48h, 48-72h, 72-96h, 96-120h, 120-144h, 144-168h, 168-192h, 192-216h and 216-240h.**

b) Cardiac assessments will be performed at Screening and on Day 1 the treatment period as:

- **Local 12-lead ECG:** A triplicate ECG will be done for assessing eligibility at screening and a single ECG will be performed for general safety at predose and at 2,5 hours post dose (inhaled administration).
- **Vital Signs - BP:** BP measurement will be performed in triplicate at the following time points: at Screening and, for general safety, at predose and at 2,5 hours post dose (inhaled administration).

3 Study Objectives

The objectives of this study are:

- To determine the absolute bioavailability of CHF6001 following single inhaled dose co-administered with an IV microtracer dose
- To characterize the mass balance and routes of elimination of CHF6001 after an intravenous (IV) microtracer dose
- To characterize the relevant metabolites in plasma, urine and feces
- To assess the safety and tolerability of the study treatment

4 Study Variables

4.1 Pharmacokinetic Variables

Following are the pharmacokinetic (PK) variables of this study:

- Plasma [¹⁴C]-CHF6001, AUC_{0-t} iv, C_{max}_iv, t_{max}_iv, AUC_{0-∞} iv, t_{1/2} iv, V_z, Vd_{ss} and CL
- Plasma [¹⁴C]-total AUC_{0-t} iv, C_{max}_iv, t_{max}_iv, AUC_{0-∞} iv, t_{1/2} iv
- Plasma CHF6001 AUC_(0-t) inh, C_{max}_inh, t_{max}_inh, AUC_(0-∞) inh, t_{1/2} inh, F_{inh}
- Urine and feces [¹⁴C]-CHF6001 and [¹⁴C]-total excreted fraction (F_{eu}, F_{ef} and F_{eu+f})
- Systemic blood clearance [¹⁴C]-CHF6001 CL_{blood}, renal plasma and blood clearance CL_R and CL_{R_blood}
- Blood to plasma ratio (R_{b/p}) [¹⁴C]-CHF6001
- Blood to plasma ratio (R_{bt/pt}) [¹⁴C]-total
- Metabolized fraction (F_{e_{met}})
- Hepatic extraction [¹⁴C]-CHF6001 (E_{h_blood})

Characterization of the relevant metabolites

For metabolites in plasma accounting for $\geq 10\%$ of total radioactivity recovered in this matrix, structural characterization may be performed, where possible. For metabolites in urine and feces (total excreta) accounting for $\geq 10\%$ of total administered radioactivity, structural characterization may be performed, where possible:

- Fraction of the relevant metabolites in plasma (Fr_{plasma}), fraction of the relevant metabolites recovered in urine and feces (Fr_{urine}, Fr_{feces}, Fr_{urine+feces})

Where possible, these data will be reported in a separate report together with structural characterization.

4.2 Safety Variables

Following are the safety variables for this study:

- AEs and ADRs
- Vital signs parameters (SBP and DBP)
- HR from 12-lead electrocardiogram (ECG)
- Laboratory parameters (haematology, chemistry and fasting glucose)

4.3 Other Variables

No other variables defined.

5 Sample Size

According to the exploratory nature of the study, no formal sample size calculation was performed. A total of 8 subjects will be included in the study to characterize the absolute bioavailability and the mass balance of CHF6001.

6 Analysis Sets

The definitions of the analysis sets are summarised below. A final agreement on the subjects to be included in or excluded from each analysis set will be reached during the Data Review Meeting (DRM) before the database lock. Inclusions and exclusions from analysis sets will be fully documented in the Data Review Report (DRR).

6.1 Safety Population

Safety Population is defined as all enrolled subjects who start study treatment inhalation.

The Safety population will be used in the analysis of all safety variables.

6.2 Pharmacokinetic (PK) Population

PK population consists of all subjects from the safety population excluding subjects without any valid PK measurement or with major protocol deviations significantly affecting PK, for example: incorrect inhalation, change in subject condition (cold), failure in delivery of the device, use of non-permitted medications.

PK variables will be analysed in the PK population.

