## **12.2 Populations for analysis**

- Safety population: **all enrolled subjects who start study treatment inhalation.**
- **PK population:** all subjects from the safety population excluding subjects without any valid PK measurement or with major protocol deviations significantly affecting PK, for example: incorrect inhalation, change in subject condition (cold), failure in delivery of the device, use of non-permitted medications. Exact definition of major protocol deviations concerning PK will be discussed by the clinical team and described in a specific document before bioanalytical data are disclosed. Subjects will not be excluded on the basis of statistical analysis or for pharmacokinetic reasons, except in the cases defined in the EMA "Guideline on the Investigation of Bioequivalence" [21].

PK variables will be analysed in the PK population. The Safety population will be used in the analysis of all safety variables.

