7.1 Statistical Significance

There is no hypothesis testing or confidence interval (CI) calculation performed hence statistical significance is not applicable.

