8.6 Compliance

Treatment Compliance

In general, treatment compliance will be evaluated on the basis of the information recorded in the eCRF.

Number of correct and incorrect inhalations, number of interruptions during the infusion will be summarized using descriptive statistics on Safety population.

In addition, all variables related to the inhalation and to the IV infusion will be listed.

9 Pharmacokinetics Analyses

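### One whole-subject PK population means that a subject excluded for a failed inhalation would also drop out of the IV and mass-balance summaries, where the data remain valid.

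*SAP*

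**What the plan says.** SAP 6.2 builds one PK population from the Safety population. It removes subjects who have no valid PK measurement, or who have "major protocol deviations significantly affecting PK, for example: incorrect inhalation, change in subject condition (cold), failure in delivery of the device"; use of non-permitted medication is the remaining example. It closes with "PK variables will be analysed in the PK population". Protocol 12.2 uses the same construction ("with major protocol deviations significantly affecting PK, for example: incorrect inhalation"). It also sets a deadline, the release of the assay results, for settling the detail: "Exact definition of major protocol deviations concerning PK will be discussed by the clinical team and described in a specific document before bioanalytical data are" […].

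SAP 4.1 puts the inhaled parameters and the IV-only parameters in one list of PK variables. SAP 6 leaves final membership of each set to the Data Review Meeting before database lock. SAP 7.9.2, writing about exclusions under the EMA bioequivalence guideline, treats leaving the PK population as leaving the PK analysis. Neither document defines an IV or mass-balance set, or confines an inhalation-related exclusion to the inhaled parameters.

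**The concern.** The study gives two doses by two routes and measures them separately: unlabelled drug by inhalation and 14C-labelled drug by infusion. Under Protocol 6.2.3.1 an incorrect inhalation is one that, in the investigator's judgement, materially reduces the dose reaching the lungs. That is a fault in one of the two doses. The analysis set does not separate them, so excluding a subject for that fault also takes the subject out of summaries that depend only on the other dose.

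Mass balance and routes of elimination form one of the four objectives and rest on the IV tracer alone. The plasma part of the metabolite objective does so too. With 8 subjects, each one is an eighth of the information. A faulty inhalation cannot be made up, because Protocol 6.2.3.1 allows no extra inhalations. Protocol 4.4 ties additional enrolment to drop-out, so it is not clear that a subject who completes after a faulty inhalation would be replaced.

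**Working it through.** There is no figure in the plan to reproduce. SAP 5 gives the size without a calculation ("A total of 8 subjects will be included in the study to characterize the absolute bioavailability and the mass balance of CHF6001"), and SAP 7.1 says "There is no hypothesis testing or confidence interval (CI) calculation performed hence statistical significance is not applicable". The check therefore has two parts: which variables a failed inhalation can affect, and what losing a subject costs.

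**Which variables use the inhaled dose** (formulas from Protocol 8 and SAP 9)

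- CL = Dose_IV / AUC0-∞ of [14C]-CHF6001. Vz and Vdss use the same IV data.
- Dose_IV comes from syringe weights before and after dosing.
- Fe in urine and feces = 100 × amount excreted / Dose_IV.
- CL_R = cumulative urinary amount / AUC0-∞ of [14C]-CHF6001.
- R_b/p and R_bt/pt are 14C blood-to-plasma ratios at 20 minutes after the start of infusion.
- Fe_met uses 14C excreted amounts only.
- E_h = (CL_blood − CL_R_blood) / Q_H, with Q_H assumed to be 87 l/h.
- Fr_plasma = 100 × AUC of the 14C metabolite / AUC of total 14C.
- F_inh = (AUC_inh × Dose_IV) / (AUC_IV × Dose_inh).

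Only F_inh, and the inhaled exposure parameters behind it, involve the inhaled dose.

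**Effect of a partial inhalation.** Protocol 6.2.1 relies on linear kinetics that do not change with time. Let d be the fraction of the inhaled dose delivered, and keep Dose_inh at the nominal 3200 µg (an assumption: the plan describes no measurement of the delivered inhaled dose). AUC_inh is then multiplied by d and AUC_IV is unchanged.

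| d | Calculated F_inh / true F_inh | Calculated CL / true CL |
|---|---|---|
| 1.00 | 1.00 | 1.00 |
| 0.75 | 0.75 | 1.00 |
| 0.50 | 0.50 | 1.00 |
| 0.25 | 0.25 | 1.00 |

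Excluding such a subject from F_inh is reasonable. Excluding the subject from CL or excretion gains nothing.

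**Cost of losing subjects, at the same SD.** The standard error going from 8 to 7 rises by the factor √(8/7) = 1.069, or 6.9%. The 95% half-width of a mean, in SD units, is t(0.975, n−1)/√n.

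| n | Half-width (SD) | Relative to n = 8 |
|---|---|---|
| 8 | 0.836 | 1.00 |
| 7 | 0.925 | 1.11 |
| 6 | 1.049 | 1.25 |

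**How often.** The documents give no rate of excluding inhalation failures. Assuming independent subjects and a rate p, the chance of at least one among 8 is 1 − (1 − p)^8:

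- p = 5%: 34%
- p = 10%: 57%
- p = 20%: 83%

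These show a range; they are not forecasts.

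**The case against.** The strongest reply is that nothing is removed automatically. The deviation must be major and must significantly affect PK. Its exact definition is left to a separate document that could deal with route, and the Data Review Meeting decides. The footnote rule in SAP 7.9.2 covers exclusion of data as well as of subjects, so the meeting could drop only the inhaled data. SAP 7.9.1 also says that no collected data are excluded from the statistical analyses. Training on three occasions, and no dosing if training fails (Protocol 6.2.4), should make failures uncommon.

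Most of this stands as a limit on the claim. A reader might infer that any failed inhalation removes the subject; the documents do not say so. But the stated rule works by whole subject, names incorrect inhalation as its first example, and gives the meeting no instruction to keep the IV data. The specific PK provisions in SAP 6.2 and 7.9.2 qualify the general statement in 7.9.1.

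Three further inferences are not supported:

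- **That an interrupted infusion would remove valid inhaled data.** Infusion interruption is not among the exclusion examples. SAP 8.6 only says that the "number of interruptions during the infusion will be summarized using descriptive statistics on Safety population", and Dose_IV is the dose actually given.
- **That the urine and feces metabolite results would lose the subject.** Profiling in those matrices is pooled across subjects (Protocol 7.2.1.2 and 7.2.1.3), the fractions go to a separate report (SAP 4.1, 9.1), and the plan does not say that the PK population governs the pools. Plasma is pooled within each subject, so the point applies there.
- **That the data would be discarded.** SAP 9.8 lists all individual concentrations and PK parameters.

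The output list in SAP 16 was not in the text available for this check, so populations named for individual outputs could not be verified.

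**Conclusion.** The point holds as a conditional one. If a failed inhalation is judged a major deviation and the subject leaves the PK population, the plan's own rule takes valid IV data out of the summaries for clearance, volumes, excretion, blood-to-plasma ratios, metabolized fraction, hepatic extraction and plasma metabolite fractions. This is a rule that gives a worse result when it is applied as written, and not merely a missing detail.

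For one subject the size is modest: summary n falls from 8 to 7 instead of staying at 8, with a standard error 6.9% larger and a half-width 11% larger. Both figures assume an unchanged SD. They illustrate lost precision only, because the study will report no confidence intervals. That the IV data stay valid rests on the linear kinetics asserted in Protocol 6.2.1. The argument covers deviations confined to the inhaled route. A non-permitted medication or a change in the subject's condition may affect IV disposition as well and would need its own judgement.

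**What to change.** In SAP 6.2, replace the single set with sets defined by route, all within the Safety population:

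- **IV/mass-balance set:** infusion received, valid 14C data, and no major deviation affecting IV disposition. Use it for the 14C plasma parameters, CL, CL_blood, Vz, Vdss, Fe, CL_R, CL_R_blood, blood-to-plasma ratios, Fe_met, E_h and Fr_plasma.
- **Inhaled set:** valid unlabelled CHF6001 data and no major deviation affecting inhaled PK. Use it for the inhaled exposure parameters.
- **F_inh:** subjects who are in both sets.

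Have the deferred document on major deviations state, for each type, which route it affects. Record the change in SAP 12, which now declares no departure from the protocol's analysis, because Protocol 12.2 defines the single population. Settle this before the bioanalytical data are disclosed, in line with Protocol 12.2, and in any case before database lock.

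The cost is a few lines in SAP 6.2 and 12, an extra row in the analysis-set table (SAP 8.1.3), and somewhat more table work. The number of subjects may then differ between parameter groups, so each table should state its set and n.
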